## **3. GENERAL CONSIDERATIONS FOR DATA ANALYSIS AND REPORTING**

This section discusses general policies to be employed in the analysis of the data from the study. Departures from these general policies may be given in the specific detailed sections of this SAP. When this situation occurs, the rules set forth in the specific section take precedence over the general policies.

### **3.1. Data Analysis**

All individual data entered into the clinical database will be presented in listings. In general, the listings will present the patients sorted by transplant number, collection day, and collection time.

Demographic, baseline characteristics, safety and efficacy variables will be summarized across the ITT population at designated time points of collection. Continuous variables (e.g., age) will be summarized using the number of observations, mean, standard deviation, median, minimum, and maximum values. Categorical variables (e.g., race) will be summarized using the number and percentage of patients in each category.

Missing data will stay missing unless an imputation rule is defined otherwise. Partially missing date/time variables will only be imputed when a derivation involving the date/time value is needed in the analysis. The imputation will be done as follows (when applicable): when the month/day is missing, July 1st will be imputed; when only the day is missing, the 15th of the month will be imputed; when time of day is the only missing element, 12:00 (out of 24 hours) will be imputed.

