## **9. EFFICACY EVALUATIONS**

### **9.1. Analysis of Primary Endpoints**

The primary endpoint is the proportion of patients with 1) an HbA1c  $\leq$  6.5% at Day 365, AND 2) free of severe hypoglycemic events (for definition see Section 2.7.2a) from Day 28 to Day 365, inclusive, following the first and the last islet transplant, respectively, with the day of corresponding transplant designated Day 0.

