#### **10.1.1. Definitions**

The following definitions will be applied consistently to the safety analysis:

Baseline (Clinical Labs, Physical Examinations)	The baseline value will be the result collected at the immediate pre-transplant work-up visit, if scheduled, or the most recent screening visit prior to the islet transplant where the lab/examination was scheduled.
Baseline (Vital Signs)	The baseline value will be the result collected at the immediate pre-transplant work-up visit. If this assessment was not obtained, then the most recent value obtained for

	the specific parameter prior to the islet infusion will be used as the baseline value.
Baseline (ECG parameters)	The baseline value will be the most recent pre-transplant value obtained.
Change from baseline	Value at the time point – value at baseline
Treatment-emergent	Any safety assessment that occurred at the onset of or after start of the first islet infusion, up to the end of 1-year follow-up after the last infusion.

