#### 10.1.5. Analyses of Adverse Events

Adverse events will be coded to the Medical Dictionary for Regulatory Activities (MedDRA) preferred terms (PT) and system organ classes (SOC) using version 17.0 or higher. All tabular AE summaries will be for treatment-emergent adverse events (TEAE). For all percentages, the number of patients in the ITT population will comprise the denominator.

An overall summary table will be developed to report, across the total safety population and by number of transplants received, starting from the day of first islet cells infusion to the end of 1-year follow-up after the last transplant, the total number of events and the number and percent of patients having at least one event and those related to treatment in the following categories:

a. Procedure Related Events

The incidence and severity of adverse events related to the islet infusion procedure including:

- Bleeding (> 2 g/dl decrease in hemoglobin concentration) identified within 24 hours post transplant.

- Portal vein thrombosis, branch or main, detected by ultrasound by the end of Day 7 (or on the first visit post-transplant if it does not fall on Day 7 exactly).
- Biliary puncture identified within 24 hours post transplant.
- Wound complication (infection or subsequent hernia) identified by the end of Day 7 (or on the first post-transplant visit if it does not fall on Day 7 exactly).
- Increased transaminase levels (> 5 times upper level of normal) identified by the end of Day 30 (or on the post-transplant visit that is closest to Day 30 if it does not fall on Day 30 exactly).

b. Immunosuppression/study drug Related Events

The incidence and severity of adverse events related to immunosuppression and/or the study drug (islets), including:

- Allergy
- Reduction in GFR (> 25% reduction in estimated GFR from baseline by Cockcroft and Gault formula:

$$eC_{Cr} = \frac{(140 - \text{Age}) \times (\text{Weight in kilograms}) \times [0.85 \text{ if Female}]}{72 \times (\text{Serum Creatinine in mg/dL})}$$

- Increase in urinary albumin excretion
- New onset microalbuminuria (albumin > 30 mg/day confirmed by 24 hour urine collection) in patients who were previously within normal limits
- For those patients with baseline microalbuminuria (30-300 mg/day), new onset overt albuminuria (greater than 300 mg/day confirmed by 24 hour urine collection)
- Sensitization evidenced by increase in PRA by at least 20% relative to baseline

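### Partial-date imputation in SAP 3.1 is not bounded by the infusion date, so it can drop post-infusion adverse events from the tables and move severe hypoglycemic events across the Day 28 to 365 window in either direction

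*SAP*

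**What the plan says.** SAP 3.1 (Data Analysis) gives the only rule for partial dates. With month and day unknown, "when the month/day is missing, July 1st will be imputed". With the day alone unknown the text runs "when only the day is missing, the 15", that is, the 15th of the known month. The rule is triggered by need: "Partially missing date/time variables will only be imputed when a derivation involving the date/time value is needed in the analysis".

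SAP 3 lets a later section depart from it, since "the rules set forth in the specific section take precedence over the general policies". Sections 9 and 10 contain no rule for a partial AE onset date or a partial date of a severe hypoglycemic event (SHE).

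Two derivations depend on such dates:

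- Treatment-emergence, which in SAP 10.1.1 closes one year past the final infusion and opens as follows: "Any safety assessment that occurred at the onset of or after start of the first islet infusion". SAP 10.1.5 restricts all AE tables to treatment-emergent events.
- The primary endpoint, in SAP 9.1, which counts SHEs "from Day 28 to Day 365, inclusive" after the first and after the last transplant, with the transplant day as Day 0.

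**The concern.** A fixed calendar date takes no account of when the patient was infused. If an event is known to have occurred in the infusion month and the infusion was late in that month, the rule assigns a date before the infusion. The event then fails the treatment-emergent definition and drops out of the AE tables. The first weeks after infusion are when procedure-related events are counted: SAP 10.1.5 sets their limits at 24 hours, Day 7 and Day 30.

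The SAP is deliberately cautious about other missing items. Missing relatedness counts as related (10.1.5), missing severity counts as grade 5 (notes to the Table 14.3.1 shell), and a missing primary endpoint is in general a failure (9.1.2). Dates have no such protection. The sensitivity comparison in 9.1.2 concerns imputed endpoint values and does not mention imputed dates.

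**Working it through.** The SAP gives no figure on this point, so there is none to reproduce. The check applies the written rules.

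**Inputs.** The 15th and 1 July rules (SAP 3.1); AE window Day 0-365 (SAP 10.1.1); SHE window Day 28-365 (SAP 9.1). Assumptions: one transplant, event days uniform, infusion on each of the 365 dates of a non-leap year.

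**Formula.** For infusion date t and true event day k, the imputed day is j = imputed(t + k) - t. The event moves out if k is in the window and j is not, and moves in if the reverse holds.

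**Single cases, day missing**

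- Infusion 20 March, AE 25 March (Day 5): dated 15 March, Day -5. Lost.
- Infusion 5 March, serious AE 2 March (Day -3): dated 15 March, Day 10. Gained.
- Infusion 20 March, SHE 20 April (Day 31): dated 15 April, Day 26. Not counted.
- Infusion 14 March, SHE 5 April (Day 22): dated 15 April, Day 32. Counted as a failure.

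**All infusion dates**

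| True timing | Move | Day missing | Month and day missing |
|---|---|---|---|
| AE, Day 0-30 | out | 1,523/11,315 = 13.5% | 5,208/11,315 = 46.0% |
| AE, Day 0-365 | out | 2,783/133,590 = 2.1% | 33,307/133,590 = 24.9% |
| AE, Day -30 to -1 | in | 1,260/10,950 = 11.5% | 4,995/10,950 = 45.6% |
| SHE, Day 28-365 | out | 2,783/123,370 = 2.3% | 33,307/123,370 = 27.0% |
| SHE, Day 0-27 | in | 1,260/10,220 = 12.3% | 4,690/10,220 = 45.9% |
| SHE, Day 366-395 | in | 1,523/10,950 = 13.9% | 5,055/10,950 = 46.2% |

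**Infusion month.** 185 of 365 infusion dates (50.7%) fall on the 16th or later. For these, every day-missing AE from the infusion to the end of that month is dated before the infusion. Across all infusion dates, 26.5% of day-missing AEs in the infusion's own calendar month are lost.

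**Year-only AEs, infusions from 2 July on (183 dates).** AE days falling in the infusion year number 183 + 182 + ... + 1 = 183 x 184/2 = 16,836, and all are lost. The total of in-window days is 183 x 366 = 66,978, so the share lost is 25.1%. Events in the following year are dated 1 July of that year, which is Day 182 to Day 364 and stays inside. For SHEs the same sums are 155 x 156/2 = 12,090 of 183 x 338 = 61,854, or 19.5%.

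**Balance for SHEs over Day 0-395.** Day missing: 2,783 out against 1,260 + 1,523 = 2,783 in. Month and day missing: 33,307 out against 4,690 + 5,055 = 9,745 in. The second comparison depends on the range of days considered. Later events can also move in: after a 10 September infusion, a year-only event on 10 November of the next year (Day 426) is dated 1 July, Day 294.

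**Effect on the primary endpoint.** One reclassified patient moves the rate by 1/50 = 2 points at N = 50, and by 1/15 = 6.7 points at the N = 15 considered in SAP 2.8.

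**The case against.** A reader might infer that the rule always favors the trial. It does not. It moves pre-infusion serious AEs into the tables, since Protocol 6.9.1 has them recorded regardless of timing, and it turns some SHEs outside the window into failures. With only the day missing, the SHE moves balance exactly. What stands is narrower. Protocol 6.9.1 records non-serious AEs only from hospitalization for the first transplant, so few exist before the infusion to offset those lost at the front edge.

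A reader might also infer that every year-only event is lost for infusions from 2 July on. Only those in the infusion year are. Nor does one moved SHE by itself turn a failure into a success: it must be the patient's only countable SHE, and HbA1c must be 6.5% or below.

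The strongest objection is practical. Early events are the least likely to lack a day. Patients stay at least 24 hours with blood tests every 8 hours and a Doppler within 24 hours (Protocol 6.6.6). They are then seen three times a week for two weeks and twice a week for two more, with AEs reviewed at each visit (6.6.7). Serious events must carry an onset date if known (6.9.5), and a monitor reviews all case report forms and queries omissions (6.12.1 and 6.12.2). Affected AEs would still appear in Listing 16.2.7a, where a non-serious AE dated before hospitalization would look wrong. All of this makes partial dates rare and some errors visible. It does not change the rule or return a dropped event to the tables.

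**Conclusion.** The point holds as a defect in a stated rule. Followed as written, SAP 3.1 dates some post-infusion AEs before the infusion and removes them from every treatment-emergent table, and no other section prevents it. The loss is about 13.5% of day-missing AEs on Day 0-30. For SHEs the error runs both ways: balanced when the day is missing, and a net movement out over Day 0-395 when month and day are missing.

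These are shares of partially dated events, not of all events. They assume uniform timing and a single transplant. The documents do not give the number of partial dates. It is probably small, so the overall effect probably is too. The documents do not support a claim of systematic bias in the primary endpoint.

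**What to change.** Add to SAP 3.1 or 10.1.1: when the known part of an AE onset date is compatible with onset on or after the first infusion, the imputed date is set no earlier than the first infusion date. The floor should be the first infusion, because that is where 10.1.1 starts treatment-emergence; protocol drugs begin before it. Comparing calendar dates keeps the 12:00 default for a missing time from undoing the floor on the infusion day.

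For SHEs with partial dates, add a sensitivity analysis of the primary endpoint that counts the event inside Day 28-365 whenever the known part of the date allows it. Making this the primary rule would be a debatable worst-case choice, since it would count some true Day 0-27 events as failures.

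The cost is one sentence, one extra analysis and simple programming. A few pre-infusion serious AEs with partial dates may be counted as treatment-emergent.

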### **3.2. Format**

The following formatting conventions will apply as specified for the data displays:

- All tables, listings, and figures will be presented in landscape orientation.
- All tables and listings will be produced using the Courier New font, with font size 10 or larger for tables and font size 9 for listings.
- Legends will be used for all figures with more than one variable or item displayed.
- Figures will be in black and white (no color).
- Specialized text styles, such as bolding, italics, shading, superscripted and subscripted text, will not be used in tables, figures, and listings.
- Only standard keyboard characters will be used in tables and listings. Special characters, such as non-printable control characters, printer specific, or font specific characters, will not be used on a table, figure, or listing. Hexadecimal derived characters may be used if they are appropriate to help display math symbols (e.g.,  $\mu$ ).
- Mixed case will be used for all titles, footnotes, column headers, and programmer-supplied formats.

### **3.3. Headers**

All tables, listings, and figures will have a header section that precedes the body of the display. The header will include:

- The protocol name, UIH002, and the population used in the data display (ITT, Safety, etc.) identified in the upper left corner.
- The number of pages, formatted as Page X of N located in the upper right corner.

- The title of the display centered on the page. The first title line will be the number of the table, figure, or data listing. Subsequent title lines will be the title (description) of the table, figure, or data listing.

### **3.4. Body of the Data Display**

The following conventions will be used within the body of the data display:

- Missing values for both numeric and character variables will be presented as blanks in a table or listing.
- All percentages will be rounded to the nearest whole number. The number and percentage of responses will always be presented in the form XX (XX) where the percentage is in parentheses.
- All summaries for categorical variables will include all categories, even if none of the patients had a response in a particular category. Additionally a “missing” category will be added to enumerate missing observations for each variable. This ensures completeness.
- All means and medians will be to one more significant digit than the measured value. Standard errors will be to two more significant digits than the measured value. The minimum and maximum will be the same as reported.
- All summary listings and CRF patient data listings will be sorted for presentation by patient and then by transplant number within patient.
- All date values will be presented as DDMMYY (e.g. 21AUG2014) format. A 4-digit year is required for all dates.
- All observed time values will be presented using a 24-hour clock HH:MM:SS format (e.g., 01:35:45, or 11:26). Seconds will only be reported if they were measured as part of the study.
- The sample size (n) shown as a summary statistic will be the number of patients with non-missing values. Additionally, the total number of patients will always be displayed.

### **3.5. Footers**

All tables, listings, and figures will have a footer section that follows the body of the data display. The footer will conform to the following conventions:

- All footnotes will be left justified and listed under the respective table, listing, or figure.
- Footnotes will be present on all pages where appropriate.
- Footnotes will be used sparingly and must add value to the table, figure, or data listing. If more than 4 footnote lines are planned then a cover page may be used if needed to display footnotes.

- The last line of the footer section will be a standard source line that indicates the name of the program used to produce the data display and the date and time of production of the data display.

#### **4. ANALYSIS POPULATIONS**

**ITT population:** Any patient in whom protocol-directed therapy (e.g., pre-transplant immunosuppression) is initiated will be included in the Intent-to-treat (ITT) population. All efficacy analyses will be on this ITT population regardless whether transplantation occurs or not.

**Safety Population:** Any patient in whom protocol-directed therapy is initiated will be included in the Safety population, which is the same as the ITT population. Patients in this population might not receive an islet transplant. All safety analyses will be on this Safety population.

#### **5. PATIENT ACCOUNTABILITY**

The disposition of patients will be summarized for all patients entered in the clinical database. The following disposition information will be summarized:

- The number and percent of patients who completed the study and the number and percent of patients who were withdrawn;
- The number and percent of patients withdrawing by reason for withdrawal;
- The number and percent of patients not reaching 1 year post first transplant henceforth determined ongoing as of April 13, 2015 and
- The number and percentage of patients included in the Intent-to-treat populations.

All percentages will use the number of patients entered into the database as the denominator. In addition, a data listing of patients withdrawn will be provided and will include for each patient: demographics (age and race), day of withdrawal relative to day of study medication, concomitant medications taken, and reason for withdrawal.

#### **6. PROTOCOL DEVIATIONS**

Protocol deviations will be evaluated for all patients entered in the database. All patients having a protocol deviation will be identified in patient data listing to be included in the Appendix of the CSR. The listing will include relevant information regarding the type of protocol deviation. Protocol deviations will include the following:

- Inclusion/exclusion criteria that were not met as reported on the Inclusion/Exclusion page of the CRF or the Study Continuation Record page of the CRF;
- Consent violations;
- Administration of prohibited medications;
- Altered protocol-specified study therapy;

## 7. TREATMENT COMPLIANCE

A patient data listing for all patients for whom there was non-compliance to the transplant and/or drug administration rules, if any, will be include in the Appendix of the CSR.

## 8. DEMOGRAPHICS AND BASELINE CHARACTERISTICS

Patient demographics and other baseline characteristics will be collected during the waiting period for islet transplant, and will be summarized descriptively using the ITT population. No inferential tests will be performed.

### 8.1. Baseline Data

Baseline data consist of demographic information and medical/physical assessments collected during the screening/waiting period. These data will be grouped into the following categories:

#### Demographic variables

- Age
- Sex
- Race (Caucasian, Black, Native American, Oriental, Other)
- Ethnicity (Hispanic, non-Hispanic)

#### Body habitus variables

- Weight (kg)
- Height (cm)
- BMI (kg/m^2)

#### Diabetes control variables

- Insulin requirement (units/kg/day)
- HbA1c
- Reduced awareness of hypoglycemia

- Frequency of severe hypoglycemic events (SHE)
- Ryan hypoglycemia severity (HYPO) score
- Fasting plasma glucose and C-peptide
- Glucose and C-peptide 90 minutes post glucose challenge (Mixed Meal Test)

### Health conditions

- Clinically significant medical histories
- Clinically significant current medical conditions
- Abnormal physical examination findings at screening
- Prior/Concomitant medication use at baseline

## **8.2. Analysis of Baseline Data**

### **8.2.1 Analysis of demographic variables**

Age will be reported in years and calculated using the formula  $\text{Age} = (\text{date of the islet transplant} - \text{the date of birth}) / 365.25$  and will be rounded to one decimal place. In the case when no transplant is done, the age at enrollment (calculated using the date of Informed Consent instead) will be used for baseline. The distribution of age at baseline will be displayed as mean, standard deviation, median, minimum and maximum.

Sex, race and ethnicity will be tabulated and counts and percents will be displayed.

### **8.2.2 Analysis of body habitus variables**

Weight, height and BMI will be summarized using mean, standard deviation, median, minimum and maximum. Weight at the immediate pre-transplant visit (see Section 17.1 Schedule of Assessments) or the last available measurement before transplant in the case when no transplant is done will be used for baseline analysis. Height is only measured at the first screening visit and will be used throughout the study. BMI is computed using the formula  $\text{BMI} = \text{weight}/(\text{square of height}) (\text{kg}/\text{m}^2)$  and will be rounded to one decimal place.

### **8.2.3 Analysis of baseline diabetes control variables**

The diabetes control variables are all continuous scale variables and will be summarized as mean, standard deviation, median, minimum and maximum.

Insulin requirement will be taken from self-reported insulin regimen on the current medication list at the point of immediate pre-transplant assessment. If a range instead of an exact dose schedule is given, the average value of the range will be used. Insulin dosing will be summarized in total units per kg per day by administration routes. If the insulin doses are

reported as units per day, the value will be divided by the patient weight (in kg) measured at the corresponding visit to derive the requirement in units/kg/day.

Reduced awareness of hypoglycemia is reported qualitatively at enrollment. The proportion of patients having reduced awareness of hypoglycemia at baseline will be summarized.

Baseline SHE frequencies will be based on records available during the time period between study enrollment and the first islet transplant. A SHE is identified as a hypoglycemic event in which the patient required assistance, including help from someone else to recognize or treat the reaction, injection of Glucagon, or use of hospital/ambulance. Additionally, either a blood glucose (BG) level under 50 mg/dL (when recorded) or recovery with juice/food/glucagon is concomitant of a SHE.

The frequency of SHE is calculated by dividing the total number of SHE by the total number of days during which the events were recorded and then multiplied by 30 to produce incidence per month. Note that the duration of time between enrollment and the first transplant may vary by patient. The frequencies of SHE will be summarized at baseline.

Baseline hypoglycemia severity will be quantified by the HYPO Score (Ryan EA, et al., 2004). The HYPO score is a scalar quantity based on patient recording of blood glucose readings and hypoglycemic events throughout the screening period prior to the first islet transplant. A hypoglycemic event occurs when a blood sugar reading is less than 54 mg/dL and a series of self-reported questionnaire items determine the severity. Points are awarded for each occurrence of documented hypoglycemia and extra points are given depending on the neuroglycopenic symptoms experienced or lack thereof. No points are awarded if there are autonomic symptoms, even if some neuroglycopenic symptoms are also present. Additional points are given for the need of outside help to either recognize or treat the event. A patient's baseline HYPO score is computed for the complete year by dividing the total score, the sum of points awarded to each hypoglycemic event reported, by the total number of days between enrollment and initial islet infusion (up to 365 days prior to the initial infusion), and then multiplying with 365. A larger HYPO score indicates greater severity. The analysis of the raw HYPO score adopts the methods for continuous scale variable.

Baseline lab test results for all the other variables will be taken from the CRF at the immediate pre-transplant assessment, if available. If a test was not scheduled for the immediate pre-transplant work-up, then the last available lab result from the screening visit prior to the first transplant will be used to represent baseline value.

For baseline Mixed Meal Test results, the proportions of patients' fasting and 90-minute C-peptide levels not exceeding the lowest detectable limit, 0.1 ng/mL, will be evaluated. C-

peptide levels reported as less than 0.1 ng/mL will be given the value 0 for any planned analyses that involve calculations based on C-peptide measures.

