6.9 Adverse Events Definitions and Monitoring

6.9.1 Adverse Event (AE)

An adverse event is any unfavorable and unintended diagnosis, symptom, sign (including an abnormal laboratory finding), syndrome, or disease which either occurs during the study, having been absent at baseline, or if present at baseline, appears to worsen.

The length of time between screening and first transplantation may be 6 months or more. Therefore, non-serious adverse events will be recorded on the case report forms (CRF) for the period starting with hospitalization for the first transplantation and during the subsequent study period because these events are relevant to the islet cell transplantation. All serious adverse events (see below) regardless of time relative to transplantation will be recorded on the case report form

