## 9.2. Analysis of Secondary Endpoints

Except for the primary analyses there are no explicit or implied hypotheses in the protocol. Changes in the secondary outcomes are of interest as they will relate to efficacy as measured by the primary outcome variable. All the secondary endpoints will be evaluated at 1 year after the first and 1 year after the last transplant, respectively, with the day of corresponding transplant always designated Day 0.

We will evaluate the proportions of patients presenting with insulin independence among all patients and among the patients who fulfilled the primary endpoint, respectively. **Insulin independence** while fulfilling the primary endpoint will be further evaluated by the following parameters:

- Absence of exogenous insulin injection reported at Day 365.
- Fasting capillary glucose level not exceeding 140 mg/dL (7.8 mmol/L) more than three times in a week (based on measuring capillary glucose levels a minimum of 7 times in a seven day period) at Day 365 ± 28 days.
- Fasting plasma glucose level ≤ 126 mg/dL (7.0 mmol/L) at Day 365 ± 28 days (if the fasting plasma glucose level is > 126 mg/dL [7.0 mmol/L], it must be confirmed in an additional one out of two measurements).
- 2-hour postprandial capillary glucose not exceeding 180 mg/dl (10.0 mmol/L) more than one out of every seven times in a week (based on measuring capillary glucose levels a minimum of 7 times in a seven day period) at Day 365 ± 28 days.
- Evidence of endogenous insulin production defined as fasting or stimulated C-peptide levels ≥ 0.5 ng/mL (0.16 nmol/L) at Day 365 ± 28 days.

Number and percent (over the total number of patients attaining primary endpoint) of patients attaining each outcome listed above will be summarized.

**Hypoglycemic episodes** will be measured by the Ryan HYPO Score (Ryan et al., 2004) derived from the number and severity of hypoglycemic episodes recorded throughout the follow-up phase from Day 28 to Day 365. Additionally the percent reduction from baseline will be reported.

**Glucose variability and hypoglycemia duration will be measured by continuous glucose monitoring system (CGMS)** for a 3-day period at three different time points: 1) at screening, 2) one year after first islet transplant, and 3) one year after last islet transplant. The following measurements and analysis will be reported:

- Mean glucose concentration
- Percent of time in the following ranges:
  - < 60 mg/dl
  - 60-140 mg/dl
  - 141-200 mg/dl

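### Read literally, the baseline HYPO score counts points from the whole wait but at most 365 days, overstating the percent reduction for patients who wait more than a year

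*SAP*

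**What the plan says.** SAP 8.2.3 (Analysis of baseline diabetes control variables) defines the baseline HYPO score in three steps.

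- **Data source.** The score is "based on patient recording of blood glucose readings and hypoglycemic events throughout the screening period prior to the first islet transplant".
- **Computation.** The numerator is every point the patient collected: "by dividing the total score, the sum of points awarded to each hypoglycemic event reported". The divisor is a count of calendar days with a ceiling placed in a parenthesis: "by the total number of days between enrollment and initial islet infusion (up to 365 days prior to the initial infusion". The last step puts the quotient on an annual scale, using a fixed factor of 365 for every patient.
- **Purpose.** The sentence that gives the formula opens: "A patient's baseline HYPO score is computed for the complete year".

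SAP 9.2 measures hypoglycemic episodes after transplant by the same score and adds: "Additionally the percent reduction from baseline will be reported". The baseline appears in Table 14.1.3, and the percent reduction after the first and after the last transplant in Table 14.2.2b.

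On the length of the wait, Protocol 6.6.3 treats the waiting list as part of screening and sets no maximum. Protocol 6.9.1 says: "The length of time between screening and first transplantation may be 6 months or more".

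**The concern.** Neither the description of the data source nor the definition of the total score limits the points in time. The limit of 365 days is attached only to the number of days. Once a wait passes 365 days, the divisor stops growing while points keep accumulating, so more than a year of points is treated as one year's worth.

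The percent reduction in HYPO score is a named secondary efficacy endpoint in a single-arm trial. Each patient's own baseline is the only comparator, so no control group carries the same error and cancels it. Taken alone, the mismatch can only raise the baseline, and it raises it most for those who waited longest.

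The severe hypoglycemic event frequency in the same SAP section has no such problem: it divides the events by the days over which they were recorded, so its two parts share one period.

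**Working it through.** The documents give no numerical HYPO result, so there is no figure to reproduce. The check is the algebra of the stated rule.

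**Inputs**
- W: days from enrollment to first infusion. No distribution or upper limit is given, so the values below are assumptions. Protocol 6.10.3 plans to recruit and transplant everyone within three years, which makes 1095 days an extreme.
- Divisor: min(W, 365), from SAP 8.2.3 read literally.
- Scaling: × 365, from SAP 8.2.3.
- c: points per day, assumed constant, with every event recorded.
- r: true proportional reduction after transplant. The follow-up score is taken to be on the same annual scale as the baseline.

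**Formulas**
- Literal baseline = c × W / min(W, 365) × 365.
- Matched-window baseline, with points and days both from the last min(W, 365) days = 365c.
- Inflation = literal / matched = max(1, W/365).
- Reported reduction for W > 365 = 1 − (1−r) × 365/W.
- Excess over the true reduction = (1−r)(1 − 365/W).

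**Example.** With c = 2 points per day, the matched baseline is 2 × 365 = 730 whatever the wait. At W = 730 the literal rule gives 2 × 730 / 365 × 365 = 1460. If nothing changes after transplant, the follow-up score is 730 and the reported reduction is 1 − 730/1460 = 50%.

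| W (days) | Inflation | Reported, true 0% | Reported, true 50% | Reported, true 90% |
|---|---|---|---|---|
| 365 or less | 1.00 | 0% | 50% | 90% |
| 400 | 1.10 | 8.8% | 54.4% | 90.9% |
| 500 | 1.37 | 27.0% | 63.5% | 92.7% |
| 548 | 1.50 | 33.4% | 66.7% | 93.3% |
| 730 | 2.00 | 50.0% | 75.0% | 95.0% |
| 1095 | 3.00 | 66.7% | 83.3% | 96.7% |

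**After the fix.** With one window for points and days, inflation is 1.00 at every W and the excess is zero.

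**The case against.** The strongest reply is that the parenthesis is a look-back window and not a bare cap. It is anchored to the infusion date, and the same sentence says the score is for a complete year. On that reading one takes the last 365 days before infusion, or fewer if the wait was shorter, for both events and days, and then annualises. Nothing is inflated. This reading is plausible and may well be what was intended. But the formula does not limit the points, and the reference to a complete year is equally explained by the scaling to 365, which also applies to shorter waits. Two programmers could derive baselines that differ twofold at 730 days.

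Other limits stand:

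- No document shows how many patients wait more than a year. The protocol speaks only of six months or more. The cap suggests that longer waits were foreseen, but not how often.
- A reader might infer from the zero-effect column that reported reductions will be inflated by a third to two-thirds. The documents do not support that. Those figures are the worst case, and the excess shrinks as the true effect grows: at 730 days it is 5 points for a true 90%. The protocol's background (4.1.2) describes freedom from hypoglycemia in one earlier series, and protection from severe hypoglycemia where islet function persisted in another, so no effect is not the planning case.
- A reader might also infer that the net bias must favor the transplant. The divisor counts calendar days whether or not a diary was kept, so unrecorded events lower the baseline and can offset the inflation. SAP 2.9 expects frequent missing diary data, though it says so about postprandial glucose.
- SAP 9.2 attaches no hypothesis to the secondary endpoints. Table 14.2.2b includes the median, and Listing 16.2.6c shows individual values after the first transplant, so an extreme baseline could be noticed.

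**Conclusion.** The rule is wrong as written. Followed literally, it gives a patient waiting W > 365 days a baseline up to W/365 times the true annual burden and overstates the percent reduction by (1−r)(1−365/W). At 730 days that is 50 points for a true 0%, 25 for a true 50% and 5 for a true 90%. The sizes rest on a constant event rate, complete diaries and assumed waits.

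If the look-back window was intended and is programmed that way, there is no bias and only the wording is at fault. The reach is limited to the baseline HYPO summary and a descriptive secondary endpoint. The primary endpoint, its confidence interval and the sample size are untouched. The documents do not support the wider conclusion that the trial's evidence of efficacy is biased.

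**What to change.** In SAP 8.2.3, state that points are summed only for events dated within the same days counted in the divisor, that is, from enrollment to first infusion and limited to the last 365 days before it, and that the quotient is then scaled to 365.

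This is one phrase and needs no new data. Patients who waited a year or less are unaffected. If the look-back window was always the intent, no result changes. Otherwise the downside is that reported reductions may become somewhat smaller for those who waited longer.
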